4.6 Funding

Is there any funding for the study?

No

Yes, with internal grants

Yes, by institutional third parties

Yes, from private third parties

4.7 Data management

Pseudonymized data will be collected using a pre-established electronic case report form (eCRF) developed using the REDCap capture tool hosted by CINECA, the Italian partner in charge of data management within the EU H2020 ORCHESTRA project. All centers will enter their data locally on the eCRF through internet connection. The principal investigator and/or her/his delegate will have access to all data in order to check for data integrity and advancement of data collection. Data sources will be clinical charts and hospital electronic records.

During all the study period, the principal investigator will inform investigators about the status of patient enrolment, follow-up, and data collection by newsletter periodically.

At the end of data collection, the principal investigator will be responsible for reviewing all data for integrity and accuracy. Queries will be generated and when necessary sent to

the local investigators for reviewing incomplete or inaccurate data. The database will be locked after fulfilment of all the queries.

4.8 Statistical Analysis Plan

Patients' characteristics will be summarized using absolute frequencies and percentages (categorical variables) and mean±standard deviation or median and interquartile range (scale variables, according to their distribution).

The prevalence of persisting SARS-CoV-2 infection among the immunocompromised patients will be obtained as the ratio of the number of patients with evidence of persisting SARS-CoV-2 infection on the total number of enrolled patients.

As for the analysis of risk factors for persisting COVID, comparisons between COVID-persistent and non-persistent patients will be carried out by means of survival analyses for all outcomes expressed as durations (time-to-event analyses). These outcomes will be compared by estimating Kaplan-Meier curves, calculating log-rank tests and multiple Cox regressions in which COVID persistence will be the main risk factor and including the confounders and effect modifiers listed below.

- Age
- Sex
- Comorbidities (Charlson Comorbidity Index)
- Underlying hematologic disease state
- Chemotherapy treatments performed
- Duration of Hospital stay
- Admissions to intensive care
- Days with central venous catheter
- Bacterial and fungal superinfections
- Vaccination status
- Previous SARS-CoV-2 infections
- Serological status (anti-SARS-CoV-2 antibodies)

Re-infection and imaging alterations rates will be calculated as the ratio of the number of events to the overall number of patients, and the comparison between persisters and non-persisters will be carried out by calculating the corresponding risk ratios. A multiple logistic regression model will assess the relationship between exposure and re-infection (image alteration) net of the potential confounders.

For secondary aims, the secondary endpoints will be described just for the patients with persisting COVID, categorical variables will be reported as number and relative

frequencies, continuous variables will be reported as mean±SD or median and IQR according with their distribution.

5. Administrative procedures and declarations

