3.3 Endpoints

The first primary endpoint variable will be the prevalence of persisting SARS-CoV-2 infection among the immunocompromised patients defined as the persistence or the recurrence of symptoms and signs (fever, dyspnea, hypoxemia, changes on chest-X ray or CT scan) and positive SARS-CoV-2 PCR ≥ 21 days after the time 0 (day of the first test positive for SARS-CoV2 infection).

The endpoints for the secondary objectives are:

- Duration of treatment carried out to address the persistent COVID-19 condition and treatment-related adverse effects.
- Duration of viral shedding, defined as the number of days between the first positive test and first negative PCR test.
- Duration of symptoms, defined as the number of days between symptoms onset and the clinical cure.
- Prevalence of imaging alterations, defined as the presence of new ground-glass and/or crazy paving and/or interstitial infiltrates at chest CT scan during the persisting infection (starting from 21 days after the first positive test until viral clearance).
- Re-infection within 120 days, define as new positive test with or without symptoms after viral clearance has been achieved.
- All-cause 120-day mortality.

4. Investigational plan

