4.3 Study design

Spontaneous international multicenter retrospective and prospective observational study.

The retrospective recruitment period will span from 1.01.2022 to the date of authorisation by hospital directorates following the Ethics Committees' approvals. This period has been established considering the prevalent diffusion of the omicron variant and its subvariants, which has led to significant changes in the clinical manifestations of COVID-19. The prospective recruitment will be carried out over the 12 months immediately following the retrospective period.

During the study period, screening for persisting SARS-CoV-2 infection and therapeutic management of all patients will be carried out by the attending physicians according to routine practice.

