4.4.3 Population size of the study and statistical power

According to the records of the Haematology Unit of IRCCS AOU of Bologna, from January 2022 to December 2022, 250 patients with underlying B cell malignancies have been diagnosed with SARS-CoV2 infection and we estimate that approximately 30% had viral shedding longer than 21 days. Thus, we deem that at the end of the study period, approximately 500 patients will be enrolled from IRCCS AOU of Bologna of which about 150 with prolonged infection. Considering the epidemiology of the other participating centers, we expect to reach an overall cohort of about 1000 immunocompromised patients with SARS-CoV-2 infection, with approximately 300 prolonged infections.

Power analysis carried out using Stata v.17.0 showed that a sample size of 1,000 allows to obtain power=80% and alpha=0.05 for a log-rank test comparing 120-days mortality, with a 300/700 allocation ratio, when the difference in mortality rates is at least 4% and mortality rate in the non-persistent COVID is as low as 3%, or when the difference in mortality rates is at least 5% and mortality rate in the non-persistent COVID is at least 4%.

Estimated sample sizes for two-sample comparison of survivor functions
 Log-rank test, Freedman method
 H0: HR = 1 versus Ha: HR != 1

alpha	power	N	N1	N2	nratio	E	delta	hratio	s1	s2	Pr_E
.05	.8	897	627	270	.43	59	2.054	2.054	.95	.9	.06503
.05	.8	1,343	939	404	.43	84	1.839	1.839	.95	.91	.06203
.05	.8	2,282	1,596	686	.43	135	1.626	1.626	.95	.92	.05902
.05	.8	4,900	3,426	1,474	.43	275	1.415	1.415	.95	.93	.05601
.05	.8	18662	13050	5,612	.43	990	1.206	1.206	.95	.94	.05301
.05	.843	.	1	1	.95	.95	.
.05	.8	561	392	169	.43	33	2.581	2.581	.96	.9	.05804
.05	.8	768	537	231	.43	43	2.31	2.31	.96	.91	.05503
.05	.8	1,140	797	343	.43	60	2.043	2.043	.96	.92	.05203

	.05	.8	1,918	1,341	577	.43	94	1.778	1.778	.96	.93	.04902	
	.05	.8	4,070	2,846	1,224	.43	188	1.516	1.516	.96	.94	.04601	
	.05	.8	15304	10702	4,602	.43	659	1.257	1.257	.96	.95	.04301	
	.05	.8	367	256	111	.43	19	3.459	3.459	.97	.9	.05105	
	.05	.8	471	329	142	.43	23	3.096	3.096	.97	.91	.04804	
	.05	.8	638	446	192	.43	29	2.737	2.737	.97	.92	.04503	
	.05	.8	933	652	281	.43	40	2.383	2.383	.97	.93	.04203	
	.05	.8	1,545	1,080	465	.43	61	2.031	2.031	.97	.94	.03902	
	.05	.8	3,221	2,252	969	.43	116	1.684	1.684	.97	.95	.03601	

s1, s2 = survival rates in groups 1 and 2
 N1, N2 = sample size required in groups 1 and 2.

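### The primary prevalence counts patients with ongoing or unknown symptoms and no PCR from day 21 as non-persistent, so it can be too low by an amount the plan gives no means of judging

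*Combined protocol and SAP*

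**What the plan says.** - **Formula.** Section 4.8 obtains the prevalence as the number of patients showing persistence, taken "on the total number of enrolled patients".
- **Case definition.** Section 3.3 requires persisting or recurring symptoms or signs together with a "positive SARS-CoV-2 PCR ≥ 21 days after the time 0", where time 0 is the first positive test.
- **Testing.** Section 4.3 says that "screening for persisting SARS-CoV-2 infection and therapeutic management of all patients will be carried out by the attending physicians according to routine practice". No PCR is scheduled at or after day 21.
- **Who is enrolled.** Section 4.4 covers both hospitalised patients and outpatients, and section 4.4.2 lists no exclusions. Section 4.4.1 requires signed consent, but sections 5.1 and 5.1.1 allow anonymised data where consent cannot be obtained, for example from deceased or untraceable patients. Section 5.1.1 limits this to the retrospective cohort.
- **Expected numbers.** Section 4.4.3 estimates that at the coordinating centre "approximately 30% had viral shedding longer than 21 days", and projects an "overall cohort of about 1000 immunocompromised patients with SARS-CoV-2 infection, with approximately 300 prolonged infections".

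The documents give no rule for patients whose day-21 status is unknown, no rule for deaths before day 21, no missing-data or sensitivity analysis for the prevalence, no re-testing rate and no precision target.

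**The concern.** Without a PCR from day 21 a patient cannot enter the numerator, yet everyone enrolled is in the denominator. A patient who still has symptoms at day 21, or whose symptoms are unknown, and who is not tested again is therefore recorded as non-persistent by default. For this group the error runs one way, and a larger sample does not reduce it.

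Two results are exposed. The first is the primary prevalence, which mixes how often infection persists with how often clinicians look for it. The second is every comparison of persistent with non-persistent patients, including the risk factors named in the primary objective (section 3.1). If testing differs by centre or between inpatients and outpatients, part of an apparent difference between the groups may reflect testing. Section 4.8 lists hospital stay, intensive care admission and catheter days as covariates, and all three could plausibly go with closer testing.

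**Working it through.** **The plan's own figures.** The expected prevalence is 300/1,000 = 30%, matching 150/500 at the coordinating centre. No precision is stated for it. The only sample-size calculation concerns 120-day mortality and can be reproduced. For survival of 97% against 93% with allocation ratio 0.43, HR = ln 0.93 / ln 0.97 = 2.383. Events = (1.960 + 0.842)² / 0.43 × [(1 + 0.43 × 2.383)/(1 − 2.383)]² = 39.1. The event probability is 0.04203, so N = 931 against the stated 933. That calculation does not bear on the prevalence; only its mortality rates are used below.

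**Precision.** 1.96 × √(0.30 × 0.70 / 1,000) = 0.0284, or 2.8 points (Wilson interval 27.2% to 32.9%).

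**Patients not assessable.** Let u be the share of enrolled patients with ongoing or unknown symptoms and no PCR from day 21, and let k be their risk of persistence relative to assessed patients. Neither is in the documents, so both are assumptions. If the formula returns 30%, the risk among assessed patients is 0.30/(1 − u), and the amount missed is u × k × 0.30/(1 − u).

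| u (assumed) | True value if k = 1 | Amount missed | Value if all u were persistent |
|---|---|---|---|
| 2% | 30.6% | 0.6 points | 32% |
| 5% | 31.6% | 1.6 points | 35% |
| 10% | 33.3% | 3.3 points | 40% |
| 20% | 37.5% | 7.5 points | 50% |
| 30% | 42.9% | 12.9 points | 60% |

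**Where the bias equals the half-width.** Setting the missed amount to 0.0284 gives:
- k = 1: u = 0.0284 / (0.30 + 0.0284) = 8.6%. If 30% is instead taken as the true value, u = 0.0284/0.30 = 9.5%. Hence about 9%.
- k = 0.5: u = 0.0284 / (0.15 + 0.0284) = 15.9%.
- k = 0.25: u = 0.0284 / (0.075 + 0.0284) = 27.5%.
- k = 0: no bias at any u.
- All persistent: u = 2.8%.

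The 30% counts viral shedding alone, whereas the endpoint also needs symptoms or signs. If the formula returned a lower prevalence, the break-even at equal risk would rise. At 20% the half-width is 2.48 points and u = 0.0248/0.2248 = 11%. At 15% it is 2.21 points and u = 0.0221/0.1721 = 13%.

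**Early deaths.** Overall 120-day mortality from section 4.4.3 is 0.7 × 3% + 0.3 × 7% = 4.2%, 0.7 × 4% + 0.3 × 9% = 5.5%, or 0.7 × 5% + 0.3 × 10% = 6.5%. If every one of these deaths fell before day 21 and left the denominator, 30% would become 0.30/0.958 = 31.3%, 0.30/0.945 = 31.7% or 0.30/0.935 = 32.1%. The shifts are 1.3, 1.7 and 2.1 points, all below the half-width. This is generous, because a patient classed as persistent cannot have died before day 21. Using only the deaths in the non-persistent group (2.1%, 2.8%, 3.5%) gives 0.6, 0.9 and 1.1 points. With deaths spread evenly over 120 days, 0.7% to 1.1% of patients die by day 21 and the shift is 0.2 to 0.3 points.

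**Unequal testing (illustration only).** If inpatients and outpatients had the same true risk but 80% and 40% respectively were tested from day 21 (assumed), the observed ratio of prevalences would be 0.8/0.4 = 2.0.

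**The case against.** A reader might infer that the primary estimate is biased downward by more than its own confidence interval. The documents do not support that. It needs roughly 9% or more unassessed at equal risk, and no re-testing rate is given.

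A reader might also infer that everyone not re-tested is misclassified. That is wrong as well. The definition needs symptoms or signs in addition to PCR, so a recovered patient is correctly non-persistent without a further test. In routine care those not re-tested may be mostly recovered, which shrinks the problem, possibly to nothing.

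Nor is counting early deaths as non-persistent necessarily an error. If the target is the proportion of all infected patients who reach persistence, death before day 21 is a competing event and the all-enrolled denominator is right.

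The models in section 4.8 enter persistence as the exposure, not the outcome, so the 2.0 above describes no model in the plan and rests on invented testing rates.

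Finally, restricting to ascertainable patients can err the other way. If 90% of persistent and 60% of non-persistent patients were ascertained (assumed), a true 30% would become 0.27/(0.27 + 0.42) = 39%, against 27% from the present formula.

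All of this stands, and it limits the claim. It does not supply the missing rule for patients with ongoing or unknown symptoms and no later PCR, and the plan reports nothing from which a reader could tell how large that group is.

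**Conclusion.** The point holds in a conditional form. As written, the formula classes patients with ongoing or unknown symptoms and no PCR from day 21 as non-persistent. That can only lower the primary prevalence or leave it unchanged, and it can distort comparisons of persistent with non-persistent patients if testing is uneven.

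The size cannot be determined from the documents. At 30% and 1,000 patients the bias passes the 2.8-point half-width at about 9% unassessed with equal risk and about 16% with half the risk, and it is zero if none of them were persistent. Early deaths alone do not reach the half-width on the plan's own mortality rates, and they are misplaced only if the target is day-21 survivors, which the plan does not say. How many early deaths would enter is also unclear, given the differing consent provisions in sections 4.4.1 and 5.1. The rule for unknown status should be settled before analysis, because it determines what the primary result can be said to estimate.

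**What to change.** In section 4.8:
1. State the target population: all infected patients, with death before day 21 as a competing event, or patients alive at day 21.
2. Classify each patient as persistent; non-persistent (negative PCR without a later positive in the same episode, or documented free of symptoms and signs from day 21); or not ascertainable (no qualifying PCR, with ongoing or unknown symptoms). Count deaths before day 21 separately.
3. Report these counts overall and by centre.
4. Present the all-enrolled prevalence with a 95% confidence interval beside the estimate among ascertainable patients, with bounds setting all not-ascertainable patients first to non-persistent and then to persistent.
5. Repeat the comparisons of persistent with non-persistent patients without the not-ascertainable group.

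The ascertainable-only estimate should accompany the all-enrolled figure and not replace it, since selective testing can push it upward.

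The cost is some SAP wording, a little more analysis and a wider stated range. The secondary endpoints in section 3.3 already need the first negative PCR, the date of clinical cure and 120-day vital status, so much of the input should exist. The case report form is not in the documents, so the sponsor should confirm that symptom status from day 21 is recorded, particularly for retrospective patients.

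### Viral-shedding and symptom durations go to Kaplan-Meier with no rule for death before clearance or cure; with deaths censored, the curves overstate the proportion cleared or cured

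*Combined protocol and SAP*

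**What the plan says.** Section 4.8 plans "survival analyses for all outcomes expressed as durations (time-to-event analyses"), comparing persistent with non-persistent patients by "estimating Kaplan-Meier curves", together with log-rank tests and Cox models that take persistence as the main risk factor.

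Section 3.3 supplies two such outcomes apart from treatment duration. Viral shedding is "defined as the number of days between the first positive test and first negative PCR test". Symptom duration is "defined as the number of days between symptoms onset and the clinical cure". "All-cause 120-day mortality" is a separate endpoint and is not linked to either duration.

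No section says what happens to a patient who dies before the negative PCR or the cure, and no competing-risk method is named. Section 4.4.3 plans for deaths in both groups. Its text covers cases where "mortality rate in the non-persistent COVID is as low as 3"% with a difference of at least 4 points, and where it is at least 4% with a difference of at least 5 points. Its table also contains 5% against 10%.

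The last paragraph of section 4.8 describes the secondary endpoints differently: in persisters only, by mean and SD or by median and IQR. It gives no rule for death either.

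**The concern.** A patient who dies still PCR-positive, or still symptomatic, will never clear or be cured. Death is therefore a competing event. The usual practice with Kaplan-Meier is to censor at death, which treats the dead as if they would have gone on to clear at the same rate as comparable survivors. One minus Kaplan-Meier then describes a hypothetical setting without deaths, and it exceeds the proportion who actually clear whenever uncleared patients die.

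At stake are the level of the shedding and symptom curves and the medians read from them, in a study whose purpose is to describe the course of persisting infection. On the planning figures the deaths are not negligible: 7% to 10% of 300 persisters is 21 to 30 deaths, and 3% to 5% of 700 non-persisters is 21 to 35.

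**Working it through.** **1. The plan's own figures.** The sample-size table is reproduced first, because its mortalities are used below. Freedman's method with allocation ratio r = 0.43:

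- HR = ln(s2)/ln(s1)
- E = (1.960 + 0.842)²/r × ((1 + r·HR)/(1 − HR))²
- N = E/Pr, with Pr = ((1 − s1) + r(1 − s2))/(1 + r)

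| Mortality, non-persisters vs persisters | HR | E | Pr | N computed | N in table |
|---|---|---|---|---|---|
| 3% vs 7% | 2.383 | 39.14 | 0.04203 | 931.3 | 933 |
| 4% vs 9% | 2.310 | 42.25 | 0.05503 | 767.7 | 768 |
| 5% vs 10% | 2.054 | 58.27 | 0.06503 | 895.9 | 897 |

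Rounding each group up gives the table exactly (for example 652 + 281 = 933). The sample size concerns mortality, where death is the event, so this point does not affect it.

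**2. Inputs for the check.** From the documents: 120 days of follow-up (section 4.5), persistence requiring a positive PCR at day 21 or later (section 3.3), and mortality of 7% and 10% in persisters and 3% and 5% in non-persisters (section 4.4.3). Assumed, because the documents give no figure: median clearance at day 35, 45 or 60 in persisters and day 7 to 14 in non-persisters, constant hazards, and no dropout.

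**3. Persisters, deaths unrelated to clearance.** Time runs from day 21, so 99 days remain. With clearance hazard λ = ln 2/(median − 21) and death hazard μ = −ln(1 − mortality)/99:

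- One minus Kaplan-Meier, deaths censored: 1 − exp(−99λ)
- Cumulative incidence: λ/(λ + μ) × (1 − exp(−99(λ + μ)))

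Example, median day 45 and 10% mortality: λ = ln 2/24 = 0.02888 and μ = 0.001064. One minus Kaplan-Meier is 1 − exp(−2.859) = 0.943. The cumulative incidence is 0.9645 × (1 − exp(−2.965)) = 0.915. The overstatement is 2.8 points.

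| Median clearance | 1 − KM, day 120 | Cumulative incidence, 7% / 10% mortality | Overstatement (points) | Shift in median (days) |
|---|---|---|---|---|
| Day 35 | 99.3% | 97.9% / 97.2% | 1.4 / 2.0 | 0.1 / 0.1 |
| Day 45 | 94.3% | 92.3% / 91.5% | 1.9 / 2.8 | 0.3 / 0.4 |
| Day 60 | 82.8% | 80.7% / 79.7% | 2.1 / 3.1 | 0.7 / 1.1 |

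Differences were taken before rounding.

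**4. Persisters, every death uncleared.** If the whole 7% or 10% die before clearance, at a constant hazard while uncleared, the day-120 cumulative incidence for medians at day 35, 45 and 60 is 0.925, 0.884 and 0.783 (7%) or 0.896, 0.859 and 0.763 (10%). The overstatement is then 4.5 to 6.8 points or 6.5 to 9.7 points, and the median shifts by 0.5 to 2.5 days. If those deaths also come at the very start, the overstatement is mortality × (1 − KM), so it cannot exceed the mortality itself: 7 to 10 points.

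**5. Non-persisters.** The same formulas over 120 days, with medians of 7 to 14 days, give an overstatement of 0.3 to 0.5 points at 3% mortality and 0.4 to 0.8 at 5%. The median shifts by at most 0.05 day. The ceiling is again the mortality, 3 to 5 points.

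**6. Which group is affected more.** A persister must survive to day 21, so uncleared deaths before then fall among non-persisters. A simulation with that rule (assumed median clearance 30 days after day 21 in persisters and about 10 days in non-persisters) gave these overstatements:

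| Underlying mortality, persisters / non-persisters | Death hazard | Persisters | Non-persisters |
|---|---|---|---|
| 7% / 3% | constant | 1.7 | 0.8 |
| 10% / 5% | constant | 2.5 | 1.1 |
| 7% / 3% | early (Weibull shape 0.6) | 1.6 | 1.6 |
| 10% / 5% | early (Weibull shape 0.6) | 2.3 | 2.5 |

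When deaths cluster early, the ordering disappears or reverses.

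**The case against.** The strongest reply is that only a sentence is missing. The plan never says that deaths are censored. With complete 120-day follow-up, patients who die uncleared could be held event-free to day 120, and Kaplan-Meier would then equal the cumulative incidence. The day-120 proportion cleared is not a listed endpoint, and the median moves little. All of this is fair, and it limits the size of the point. It does not remove it: section 4.8 asks for curves, censoring at death is what an analyst would normally do, and without a rule different analysts could reach different results.

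Three stronger readings are tempting, and the documents do not support them.

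- *The log-rank and Cox comparisons are invalid.* They are not. With deaths censored they validly compare cause-specific hazards of clearance or cure. The bias lies only in reading one minus Kaplan-Meier as a probability. Gray's test answers a different question, so preferring it is a choice of estimand.
- *The error must be larger in persisters because more of them die.* Step 6 shows that this depends on when deaths occur. The 7% to 10% figures are also alternatives in a grid of detectable differences, not observed or forecast mortality.
- *The error is close to 10 points.* That requires every persister death to occur uncleared, and nothing in the documents supports so extreme a pattern.

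**Conclusion.** The point stands as a moderate fault in the choice of estimator. With deaths censored, the planned Kaplan-Meier curves overstate clearance and cure in both groups. Under roughly constant hazards and the planning mortalities, the day-120 overstatement for shedding is about 1 to 3 points in persisters, with a ceiling of 7 to 10, and under 1 point in non-persisters. Early deaths could raise the non-persister figure to the level seen in persisters. Median shedding in persisters shifts by 0.1 to 1.1 days if deaths are unrelated to clearance, and by up to about 2.5 days in the all-uncleared case of step 4.

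The direction follows from the estimator. The sizes rest on assumed clearance times, assumed death patterns and planning mortalities, and would grow with higher mortality. Symptom duration has the same defect, but its size was not calculated separately.

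**What to change.** In section 4.8, for viral shedding and symptom duration:

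- State how death before clearance or cure is handled.
- Replace the Kaplan-Meier curves with Aalen-Johansen cumulative incidence curves with death as the competing event, and take medians from those curves.
- Keep log-rank and Cox with deaths censored, label them as cause-specific comparisons of clearance or cure, and report the cause-specific hazard for death alongside. Gray's test may be added as a supplement.
- Keep Kaplan-Meier for all-cause 120-day mortality.
- Reconcile the between-group plan with the last paragraph of the section, which describes secondary endpoints in persisters only.

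The cost is SAP wording and standard software commands. Clearance, cure and death are already endpoints, so no new data are needed.

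This does not cure a separate problem. The groups are partly defined by PCR positivity at day 21 or later, so comparing shedding from day 0 is partly circular and carries immortal time. A day-21 landmark would address the immortal time; a competing-risk method alone would not.

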4.5 Study duration

The study will be composed by:

- a prospective recruitment period of 1 year after Ethics Committees' approvals and directorates' permissions to conduct the study (during which retrospective data will also be collected);
- Follow-up period of 120-days from the diagnosis of SARS-CoV-2 infection;
- Data collection and analysis, that will last 6 months

For an overall duration of approximately 22 months

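### Persistence is known only from day 21, yet persisters and non-persisters are compared on 120-day mortality with no landmark, time-dependent exposure or rule for earlier deaths, which invites immortal-time bias

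*Combined protocol and SAP*

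**What the plan says.** - **Exposure.** Section 3.3 defines persistence as "the persistence or the recurrence of symptoms and signs" together with "positive SARS-CoV-2 PCR ≥ 21 days after the time 0", time 0 being the first positive test.
- **Outcome and follow-up.** Section 3.3 lists "All-cause 120-day mortality" as a secondary endpoint. Section 4.5 gives a "Follow-up period of 120-days from the diagnosis of SARS-CoV-2 infection". Section 4.4.2 has no exclusion criteria.
- **Analysis.** Section 4.8 compares persistent and non-persistent patients on outcomes expressed as durations by Kaplan-Meier curves, "calculating log-rank tests and multiple Cox regressions in which COVID persistence will be the main risk factor". It does not name mortality.
- **Sample size.** Section 4.4.3 supplies the link to mortality. Its power statement is for "a log-rank test comparing 120-days mortality, with a 300/700 allocation ratio", with 3% v 7% as the first scenario.
- **Prevalence.** Section 4.8 divides "the number of patients with evidence of persisting SARS-CoV-2 infection on the total number of enrolled patients".
- **Testing and consent.** Testing follows routine practice (section 4.3). Prospective patients enrol only with consent, and retrospective consent is sought at follow-up visits (section 5.1.1). Section 5.1 says data on deceased or untraceable patients will be collected anonymously; section 5.1.1 says only that such data may be recorded.

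No section gives a landmark, delayed entry, a time-dependent exposure, a time origin for the mortality analysis, or a rule for patients who die before day 21.

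**The concern.** A patient who dies before day 21 cannot meet the definition of persistence. The natural reading is that time runs from diagnosis, groups are fixed, and anyone without evidence of persistence is non-persistent. This is an inference, but the prevalence formula points the same way. On that reading every persister is guaranteed to survive to the qualifying date, and all early deaths are counted against the comparator. Covariate adjustment does not repair this, because the fault lies in when exposure is assigned. The guaranteed period can run past day 21, since recurrence counts and swabs are unscheduled.

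The mechanism pulls the hazard ratio for persistence down. It can hide a real excess of deaths or make persistence look protective. Other features, such as selective retesting of sicker patients, could push the other way, so the net direction is not claimed. Mortality is a secondary endpoint, but the sample size of 1,000 is justified by this comparison.

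**Working it through.** **1. The plan's own figure.** Inputs from section 4.4.3: two-sided alpha 0.05, power 80%, allocation ratio k = 0.43, survival 0.97 and 0.93, Freedman method.

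- HR = ln 0.93 / ln 0.97 = 2.383
- E = (1.960 + 0.842)² / k × [(1 + k·HR)/(HR − 1)]² = 39.1
- Probability of death = (0.03 + 0.43 × 0.07)/1.43 = 0.0420
- N = 39.1/0.0420 = 931, against 933 stated. For 4% v 9% the result is 768, against 768 stated.

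With 700 and 300 patients, 42 deaths are expected (21 + 21). Power = Φ{(HR − 1)/(1 + k·HR) × √(k·E) − 1.96} = 83%. The plan's arithmetic is sound; the question is what it is applied to.

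**2. Assumptions.** The documents do not give the share f of deaths before day 21. Values of 10%, 17.5% (21/120, a constant rate) and 30% are used. Everyone is taken to qualify on day 21. Two readings of 3% v 7% are possible:

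- (A) mortality in the groups patients would belong to if all could be classified;
- (B) mortality in the groups as classified.

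**3. Reading A, groups fixed from diagnosis.** Let e1 and e0 be the early deaths among would-be persisters and non-persisters. With the same early share in each group, e1 = 300 × 0.07 × f and e0 = 700 × 0.03 × f. With equal early risk, e1 = 300 × f × 42/1000 and e0 = 700 × f × 42/1000. All early deaths are counted as non-persistent.

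Worked case, f = 17.5%, same share: e1 = e0 = 3.675.

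- Persisters: (21 − 3.675)/(300 − 3.675) = 17.325/296.325 = 5.8%
- Non-persisters: (21 + 3.675)/(700 + 3.675) = 24.675/703.675 = 3.5%
- HR = ln(1 − 0.0585)/ln(1 − 0.0351) = 1.69; power 39%

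| Early deaths f | 10% | 17.5% | 30% |
|---|---|---|---|
| Same share: HR (power) | 1.96 (60%) | 1.69 (39%) | 1.30 (13%) |
| Equal risk: HR (power) | 2.12 (70%) | 1.94 (59%) | 1.67 (38%) |
| Same share, half of early deaths captured | 2.15 (70%) | 1.98 (57%) | 1.69 (34%) |
| Equal risk, half captured | 2.34 (79%) | 2.30 (75%) | 2.23 (69%) |

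Simulation (3,000 runs per cell) gives 57%, 39% and 14% for the first row and 68%, 56% and 37% for the second.

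**4. No true difference (4.2% in both groups).** The simulated test from diagnosis finds persistence falsely protective in about 5%, 9% and 22% of runs, or 3.3%, 4.7% and 9.4% with half of early deaths captured. The nominal rate is 2.5%. A day-21 landmark gives 1.9–2.3%.

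**5. Later qualification.** If qualifying dates spread evenly over days 21–42 (assumed), simulated power from diagnosis at f = 17.5% and 30% is 20% and 5% (same share) or 32% and 18% (equal risk).

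**6. A different model.** Assume a common hazard before day 21, with 30% of day-21 survivors becoming persisters. At 17.5% and 30% of the hazard before day 21, a true HR of 2.38 appears as 1.82 and 1.47, and a true HR of 1 as 0.76 and 0.62.

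**7. Reading B.** Planned power stays about 83%, because the assumed rates already contain the misallocated deaths. The contrast between groups is still biased.

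**The case against.** The strongest reply is that the plan never states the faulty analysis. Section 4.8 applies survival methods to outcomes expressed as durations, without naming mortality, and closes by saying that secondary endpoints are described only in persisters. The prevalence denominator does not assign anyone to a comparator in a Cox model. This stands as a limit on the claim: the omission is certain, while the bias follows from the natural reading. It does not remove the point. Section 4.4.3 names both test and endpoint, and section 3.2 plans the comparison. If the descriptive sentence governs, the justification for 1,000 patients supports no planned analysis.

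Second, reading B is arguably the more direct reading of section 4.4.3, and every power loss above needs reading A. That is fair, so both readings are shown. Bias is present under either.

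Third, the size rests on assumed early-death shares, and the 30% in section 4.4.3 describes viral shedding alone, whereas section 3.3 also requires symptoms or signs. This stands too: the figures are illustrations, not estimates.

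Fourth, few early deaths may be captured. Half capture shrinks the bias without removing it, and the sentence in section 5.1 on deceased patients makes their entry more likely.

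**Conclusion.** The concern holds. Exposure is defined by events on or after day 21, follow-up starts at diagnosis, nobody is excluded, and nothing in the plan handles the interval between. Analysed as fixed groups from diagnosis, the mortality comparison carries immortal-time bias that lowers the hazard ratio.

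The size is not identified from the documents. Under reading A with 17.5% of deaths before day 21, all captured and everyone qualifying on day 21, the HR of 2.38 becomes 1.69–1.94. Over the full range examined, including half capture, it runs from 1.30 to 2.34. Under reading B power is unaffected but the estimate is not. The point should be fixed before analysis. It does not touch the prevalence endpoint, but it bears on the comparison that justifies the sample size.

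**What to change.** - In the mortality analysis, enter persistence as a time-dependent covariate that switches on the day the section 3.3 definition is first met.
- As an alternative or sensitivity analysis, use a landmark at the end of a prespecified classification window long enough for routine testing dates. Include patients alive then, with status fixed by data up to that day.
- State the time origin for mortality and how deaths before day 21 are classed. Report earlier deaths separately for the retrospective and prospective cohorts, with the number entered without consent.
- Say which groups 3% and 7% describe (would-be groups, groups as classified, or deaths after classification), and restate power for the chosen analysis.
- Reconcile the sentence in section 4.8 limiting secondary endpoints to persisters with sections 3.2 and 4.4.3.

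**Cost.** SAP wording, a new power statement and one derived date. That date comes from unscheduled swabs, partly in retrospective charts. It should be captured at entry, because anonymised records have no key for tracing it later. Selective retesting is not cured by this change.

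Deaths before the landmark leave the comparison. At f = 17.5% and 30%:

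| Analysis (reading A) | Same share | Equal risk |
|---|---|---|
| Day-21 landmark, all qualify on day 21 (Freedman) | 75%, 69% | 89%, 93% |
| Time-dependent, qualifying days 21–42 (simulated) | 68%, 61% | 82%, 85% |
| Day-42 landmark, qualifying days 21–42 (simulated) | 65%, 57% | 78%, 82% |

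Under reading B a day-21 landmark gives about 98% and above 99%. That comes from assigning every early death to the non-persisters, which implies a post-landmark HR of 3.6 and 5.9, so it should not be counted on as a gain.
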